## 19.0 Potential Benefits to Subjects

### 19.1 \* Will participation in this study provide direct benefits to the subject?

Yes  No

### 19.2 If Yes, describe the potential direct benefits:

Volunteers will receive without cost an FDA-approved vaccine.

## 20.0 Potential Risks to Subjects

### 20.1 \* Describe any potential risks: physical, psychological, social, legal or other and assess their likelihood and seriousness. Indicate risks both to the subjects and to the embryo or fetus if the subject is or may become pregnant. Please provide the potential risks below:

#### Influenza Vaccine (IM administration):

- Most common ( $\geq 10\%$ ) injection-site reactions were injection site tenderness, pain, swelling and arm stiffness.
- Most common ( $\geq 10\%$ ) systemic adverse events were headache and myalgia.
- Life-threatening allergic reactions from vaccines are very rare. If they do occur, it is usually within a few minutes to a few hours after the shot.
- In 1976, a type of inactivated influenza (swine flu) vaccine was associated with Guillain-Barré Syndrome (GBS). Since then, flu vaccines have not been clearly linked to GBS. However, if there is a risk of GBS from current flu vaccines, it would be no more than 1 or 2 cases per million people vaccinated. This is much lower than the risk of severe influenza, which can be prevented by vaccination. Potential risks associated with venipuncture include discomfort or pain, ecchymosis, bleeding, phlebitis and infection at the needle insertion site. Additional risks include lightheadedness and a vasovagal response. Psychological affect of MetS diagnosis although this will be presented as a positive to be aware and to make healthy life style changes .

## 21.0 Procedures to Minimize Risks

### 21.1 \* Describe the procedures for protecting against or minimizing any potential risks, and include an assessment of their likely effectiveness. Include a discussion of confidentiality safeguards, where relevant, and arrangements for providing medical treatment, if needed.

Study volunteers will be monitored for a minimum of 20 minutes after receiving their vaccination  
All blood will be drawn by trained professionals using sterile technique  
The influenza vaccine will be administered by an RN or LIP.  
Persons with allergy to eggs will be excluded from the study  
Persons with a history of Guillian-Barre' syndrome will be excluded from the study.

## 22.0 Alternative Methods or Treatments

### 22.1 \* Describe alternative methods or treatments for the disease(s) under study, if any, that were considered and why they will not be used:

**they will not be used:**

The study participant can obtain an influenza vaccine from other sources, such as from their PCP, pharmacies, clinics.

### 23.0 Data and Safety Monitoring

**This section describes the Data and Safety Monitoring Plan (DSMP) required of each protocol undertaken at the CCTS according to HRPP and NIH policies Notice 98 -084 and Notice 00-038, as cited in Help Sections below. Depending on the level or risk and trial phase, some protocols will need Data and Safety Monitoring Boards.**

#### 23.1 \* Overall Risk Classification

**An estimate of risk is necessary to evaluate the adequacy of the planned monitoring. The HELP section provides guidance in making the risk assessment.**

**Read the risk definitions and examples of risk in the HELP section and select the risk category that best describes the current study.**

**If your assessment differs from the definitions the HELP section, describe any factors that modify your judgment of the overall risk in the text box after the risk designation.**

- MINIMAL RISK  
 LOW RISK  
 MODERATE RISK  
 SIGNIFICANT RISK

Please provide any optional description(s):

#### 23.2 Protocols Involving Minors

The chance of direct benefit to the child, or to understanding a disorder not otherwise understood, may be major factors in justifying more than minimal risk in research involving children.

Based on the above definitions, please specify your study's risk classification below:

- NOT GREATER THAN MINIMAL RISK (the risk of daily life to a healthy child living in a safe environment) 45 CFR 46.404  
 GREATER THAN MINIMAL RISK WITH DIRECT BENEFIT TO SUBJECT; 45 CFR 46.405  
 GREATER THAN MINIMAL RISK, NO DIRECT BENEFIT, BUT BENEFIT TO UNDERSTANDING OF SUBJECT'S DISORDER; 45 CFR 46.406  
 RESEARCH NOT OTHERWISE APPROVED PRESENTING OPPORTUNITY TO UNDERSTAND, PREVENT OR ALLEVIATE SERIOUS PROBLEM AFFECTING CHILDREN 45 CFR 46.407 (cannot be approved by IRB; requires public comment)

#### 23.3 DSMB

- The NIH requires that all SIGNIFICANT RISK protocols have a **Data and Safety Monitoring Board** and provide information about the expertise and independence of that Board
- Phase III trials require a Data and Safety Monitoring Board,
- A DSMB may be appropriate for some Phase I and II protocols. (See Help for examples.)
- It is the investigator's responsibility to report to the IRB, the findings and recommendations of the DSMB as they become available.

Please specify:

- A DSMB is required for this study  
 A DSMB is not required for this study  
 Unsure

If a DSMB is required, please indicate why:

- Significant Risk  
 Study Design - Phase III  
 Study Design - Placebo Controlled  
 Study Design - Multicenter Trial  
 Study Design - Other Factor

If other factor, please specify:

Other factors, please specify:

If a DSMB is required, select one:

- An independent DSMB has been constituted; the members, mission charter, schedule for meetings, and a listing of the data to be reviewed by the DSMB will be attached.
- A DSMB has not yet been constituted; the PI will consult the IRB and/or CRSO for assistance in assembling a DSMB.

If a DSMB is not required, but is being constituted for other reasons, please explain:

### 23.4 \* Safety Review

Select one:

- Safety Review is conducted as follows: Laboratory results for research volunteers will be reviewed in a timely manner, usually within 24 hours of receipt by a licensed practitioner. The potential clinical significance of any abnormal finding will be documented in the medical and research record(s), and an appropriate plan or referral developed. The PI's review of safety issues at research team rounds will be documented in the meeting minutes.
- Protocol Specific

If Protocol Specific, please describe safety review for protocol tests and procedures that require other than routine review. For example, an EKG taken to detect emerging conduction problems might require immediate safety review.

### 23.5 Monitoring

Monitoring Personnel: See Help Bubble to the right.

#### Internal Monitoring

The PI or his/her designee shall conduct internal monitoring to assure the safe and proper conduct of the protocol and all the elements list above in monitoring, following the general principles of quality management. The intensity and frequency of internal monitoring will depend on the protocol risk to subjects, the experience of the PI and research team, rate of enrollment, and specific details of the protocol.

Internal monitoring of informed consent and eligibility documentation will be conducted by the research team shortly after enrollment begins. Internal monitoring activities will be documented by logs, meeting minutes or other systematic means.

Specify the research team members who will conduct the internal monitoring of the study (see Help for who may monitor):

[name], [name]

For new investigators: Internal monitoring should be conducted at least monthly by new investigators until there are essentially no findings to correct at each review.

#### External Monitoring

\* Is external monitoring planned for this protocol?

- Yes
- No
- Unsure

If external monitoring is planned, please specify (see Help for who may monitor):

- (Significant Risk) External monitoring will occur at least every six weeks unless there is no enrollment
- (Moderate Risk) External monitoring will occur at least quarterly
- (Low or Minimal Risk) External monitoring will occur at least annually

If external monitoring is planned, please specify the name of the monitor:

CRSO will determine the monitor for this study

- Note that copies of external monitoring reports must be supplied to the IRB and the CRSO as soon as they are made available

Additionally, audits of the research records of minimal, moderate or significant-risk protocols may be performed by the CRSO staff on a random basis or as part of a prospectively identified auditing plan.

### 23.6 Adverse Event Classification

Adverse events are classified by definition, severity, and association with the investigational trial.

#### Definition of an Adverse Event

Any unfavorable or unintended sign (including abnormal lab findings), symptom or disease temporally associated with the use of a medical treatment or procedure, or protocol, regardless of whether it is considered related to the medical treatment or procedure or protocol.

#### Definition of a Serious Adverse Event

Any unanticipated event that involves the following:

- results in death
- is life-threatening
- requires hospitalization or prolongs existing hospitalization
- results in persistent or significant disability/incapacity

o is any medical event which requires treatment to prevent one of the outcomes listed above  
Other events can be classified as "serious adverse events" at the discretion of the PI.

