### **Definition of Anticipated/Expected Adverse Event**

Any adverse event, which has been reported in the Investigator's Brochure, package insert, safety reports, clinical protocol, consent form or listed in the NCI agent-specific Expected Adverse Event List, is classified as an expected adverse event. The investigator must provide the available data of known adverse events and toxicities that have been associated with the study drug, device, intervention, or procedures. This information helps to define the level of risk of the trial and enables safety monitoring. A minimal risk trial may not have any defined risks and a statement to that effect is sufficient to meet the DSMP requirements.

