#### Definition of an Unanticipated/Unexpected Adverse Event

Any adverse event that is not consistent with the known, predicted possible effects of the research protocol. An unexpected adverse event varies in nature, intensity or frequency from information on the investigational product provided in the Investigator's Brochure, package insert, safety reports, clinical protocol, or listed in the consent form.

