## **23.7 Reporting Adverse Events**

**All AEs will be reported to the IRB at least annually.**

### **Reporting Serious AEs**

- Serious Adverse Events, (SAEs) will be reported to the IRB according to policy, within two working days of identification of the SAE.

Select all that apply:

- SAEs will be reported to the Sponsor and or ESCROW

SAEs will be reported to the sponsor within how many days of the event?

- SAEs will be reported directly to the FDA, per 21 CFR 312

SAEs must be reported directly to the FDA within 7 days of the event by the investigator/sponsor.

- SAEs will be reported to another entity

Describe:

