### 24.0

#### Toxicity Management and Stopping Rules

**24.1 \* Describe any drug toxicity or other conditions under which the participation of a subject or the conduct of the study would be stopped in order to maximize safety (e.g., toxicity management and stopping rules):**

A severe allergic reaction to the Flu vaccine.

\* Indicate withdrawal criteria and procedures below:

Volunteers may be involuntarily withdrawn from this study if they experience a significant adverse event.

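### The SAE definition requires an event to be unanticipated, so a serious event already listed as a risk has no mandatory prompt report to the IRB

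*Combined protocol and SAP*

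**What the plan says.** Section 23.6 gives the SAE definition as "Any unanticipated event that involves the following". The criteria listed are death, threat to life, hospitalization or its prolongation, persistent or significant disability, and events needing treatment to prevent one of these. A closing sentence lets the principal investigator class other events as SAEs at discretion.

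The same section defines expectedness separately. An adverse event already reported in the investigator's brochure, package insert, safety reports, protocol or consent form "is classified as an expected adverse event". An unexpected event is "Any adverse event that is not consistent with the known, predicted possible effects of the research protocol", and may differ from the listed information in nature, intensity or frequency.

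Section 20.1 lists the vaccine's risks. It says that "Life-threatening allergic reactions from vaccines are very rare", and of Guillain-Barré syndrome that, if there is a risk, "it would be no more than 1 or 2 cases per million people vaccinated". Section 24.1 gives one specific condition for stopping: "A severe allergic reaction to the Flu vaccine".

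Sections 23.7 and 23.8 set the reporting times to the IRB:
- SAEs: two working days from identification.
- Unanticipated adverse events that are related and worse than moderate: two working days.
- Unanticipated problems: five working days.
- Everything else: "All AEs will be reported to the IRB at least annually".

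**The concern.** Seriousness describes the outcome of an event. Expectedness describes whether the study documents foresaw it. Section 23.6 otherwise keeps the two apart, and 23.7 has its own rule for unanticipated events. Making *unanticipated* part of the SAE definition merges them, so every prompt route to the IRB then depends on the event not being foreseen.

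The events that lose a mandatory prompt report are the serious risks the protocol identified in advance. One of them overlaps with the only specific event named in 24.1. What is at stake is how soon the IRB hears of such an event. In addition, any SAE tally compiled strictly under 23.6 would leave out listed serious events.

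**Working it through.** The plan states no figure to reproduce. The check follows one event, a life-threatening allergic reaction to the vaccine, through the protocol's own definitions and reporting rules.

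| Step | Rule | Result |
|---|---|---|
| 1 | 20.1 lists the reaction as a vaccine risk | It is reported in the protocol |
| 2 | 23.6, expected event: any adverse event listed in the protocol | Expected |
| 3 | 23.6, SAE: must be unanticipated and meet a seriousness criterion | Meets the criterion but not the qualifier, so not an SAE by definition |
| 4 | 23.7, SAEs within two working days | Not mandatory |
| 5 | 23.7, unanticipated events within two working days if related and worse than moderate | Not mandatory while the event is classed as expected |
| 6 | 23.8 with the definition of an unanticipated problem in 23.6: five working days, all three criteria needed, the first being that it was not expected | Not mandatory while the event is classed as expected |
| 7 | 23.7, all adverse events at least annually | Mandatory |

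The text leaves two ways back to prompt reporting:
- The investigator may use the discretion clause in the SAE definition. This permits a two-day report but does not require one.
- The event may be argued to be unexpected because its frequency or intensity departs from what is listed. One case in 40 is 1/40 = 2.5%. For Guillain-Barré syndrome the protocol's upper figure is 2 per million, so the ratio is 0.025 / 0.000002 = 12,500. The argument is open, but the expected-event definition covers any listed event and points the other way.

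The optional lines in 23.7 on reporting to a sponsor, the FDA or another entity use the same two terms, SAE and UAE. Whichever of them were selected, they inherit the same definitions.

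How often this could matter can be gauged only for Guillain-Barré syndrome. The chance of at least one case in n vaccinated is 1 − (1 − p)^n:
- n = 40 (evaluable target, 12.7), p = 1 to 2 per million: 0.00004 to 0.00008.
- n = 100 (all who may sign consent, 12.8, an upper bound on the number vaccinated): 0.0001 to 0.0002.

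For allergic reaction the documents give only *very rare*, so no probability can be computed.

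With *unanticipated* removed, step 3 makes the event an SAE on its seriousness alone, step 4 applies, and steps 5 and 6 keep their separate role for unexpected events.

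**The case against.** A reader might infer that a listed serious event cannot reach the IRB within two days, or that no two-day route can apply to it. The documents do not support that. The discretion clause can bring any event into SAE reporting, and the definition of an unexpected event has a frequency and intensity limb that a single case of a very rare reaction could well satisfy. This stands: the event is outside *mandatory* prompt reporting, not barred from it. Prompt notice should still not depend on discretion or on settling a conflict between two definitions.

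A reader might also infer that the one event meant to halt the trial goes unreported. Section 24.1 does not say so much. Its prompt covers stopping either a subject's participation or the study, and the answer does not say which. It also speaks of a severe reaction, where 20.1 speaks of a life-threatening one. The two overlap without being identical, and the point applies to the overlap.

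Guillain-Barré syndrome is a weaker example. Section 20.1 says that later vaccines have not been clearly linked to it, and a history of it is an exclusion.

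Safety oversight does not rest on this definition alone. Vaccinees are watched for at least 20 minutes (21.1), and adverse events are assessed at every visit from the second screening visit onward (11.7). These measures serve detection and do not set a time for telling the IRB.

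Finally, SAEs are to be reported according to an IRB policy that is not in the documents and may be broader, and the definitions may be standard form wording. Both are possible. Neither cures the text, because the two-day rule applies to SAEs and this protocol defines that term itself.

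**Conclusion.** The point holds as a defect in a definition. A serious event already listed in the protocol, package insert or consent form has no assured two-day or five-day report to the IRB. The only unconditional requirement is the report made at least annually. For such an event the required time moves from two working days to as much as about 12 months.

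This rests on reading the SAE definition literally, on reading the expected-event definition as the meaning of *anticipated* (its heading uses both words), and on no unseen policy overriding the protocol's wording. The practical reach is small: about 40 people are to be vaccinated and the listed serious risks are described as very rare. The planned analyses in 11.8 and 11.9 use antibody titers, response rates and gene expression, not SAE counts, so no efficacy result changes. It is worth correcting because the affected events are the serious ones the protocol foresaw, and correction costs almost nothing.

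**What to change.** In the SAE definition in 23.6, replace *unanticipated event* with *adverse event*. Leave expectedness to the expected, unexpected and unanticipated-problem definitions in 23.6 and to the reporting rules for unanticipated events and problems in 23.7 and 23.8. The two-day rule in 23.7 then covers every serious event, listed or not. If the wording belongs to an institutional form that the team cannot edit, a sentence in 23.7 saying that SAE reporting applies regardless of expectedness would do the same.

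The wording of 20.1 and 24.1 (life-threatening against severe) should be reconciled at the same time, so that it is clear whether they refer to the same event.

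The cost is one wording change in an amendment and very few, probably no, extra SAE reports. Visits, sample size and planned analyses are unchanged.

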### **Definition of Anticipated/Expected Adverse Event**

Any adverse event, which has been reported in the Investigator's Brochure, package insert, safety reports, clinical protocol, consent form or listed in the NCI agent-specific Expected Adverse Event List, is classified as an expected adverse event. The investigator must provide the available data of known adverse events and toxicities that have been associated with the study drug, device, intervention, or procedures. This information helps to define the level of risk of the trial and enables safety monitoring. A minimal risk trial may not have any defined risks and a statement to that effect is sufficient to meet the DSMP requirements.

#### Definition of an Unanticipated/Unexpected Adverse Event

Any adverse event that is not consistent with the known, predicted possible effects of the research protocol. An unexpected adverse event varies in nature, intensity or frequency from information on the investigational product provided in the Investigator's Brochure, package insert, safety reports, clinical protocol, or listed in the consent form.

#### Definition of an Unanticipated Problem (UaP)

A UaP is an event or circumstance that meets all the following three criteria: [1] the nature, severity, frequency of the event(s) or information was not expected in the descriptions in the study documents or the characteristics of the subject population being studied; [2] there is a reasonable possibility that the procedures involved in the research caused or are linked in a significant way to the problem; [3] the event or information suggests that the research places subjects or others at a greater risk of harm than was previously known or recognized (including physical, psychological, economic, or social harm).

### **Grade and Relatedness of Adverse Events:**

Adverse Events are graded for severity and scored for relatedness to the protocol, according to a published scale. Several standardized AE Reporting scales are available. (See Help for links to these scales.)

\* Please indicate the scale you intend to use:

- CTC v2.0 ( <http://ctep.info.nih.gov/reporting/ctc.html> )
- CTCAE v3.0 ( [http://ctep.info.nih.gov/protocolDevelopment/electronic\\_applications/docs/ctcae3.pdf](http://ctep.info.nih.gov/protocolDevelopment/electronic_applications/docs/ctcae3.pdf))
- CTCAE v4.0 ([http://evs.nci.nih.gov/ftp1/CTCAE/CTCAE\\_4.03\\_2010-06-14\\_QuickReference\\_8.5x11.pdf](http://evs.nci.nih.gov/ftp1/CTCAE/CTCAE_4.03_2010-06-14_QuickReference_8.5x11.pdf))
- AIDS Clinical Trials Group (<http://aactg.s-3.com/>)
- Other

If Other, please specify:

## **23.7 Reporting Adverse Events**

**All AEs will be reported to the IRB at least annually.**

### **Reporting Serious AEs**

- Serious Adverse Events, (SAEs) will be reported to the IRB according to policy, within two working days of identification of the SAE.

Select all that apply:

- SAEs will be reported to the Sponsor and or ESCROW

SAEs will be reported to the sponsor within how many days of the event?

- SAEs will be reported directly to the FDA, per 21 CFR 312

SAEs must be reported directly to the FDA within 7 days of the event by the investigator/sponsor.

- SAEs will be reported to another entity

Describe:

### **Reporting Unanticipated AEs:**

Select all that apply:

- UAEs will be reported to the IRB

UAEs that are related and greater than moderate severity must be reported to the IRB according to policy, within two working days of identification of the UAE.

- UAEs will be reported to the Sponsor

UAE will be reported to the sponsor within how many days of the event?

UAEs will be reported to the FDA, per 21 CFR 312

UAEs will be reported to the FDA, per 21 CFR 312, within 15 days.

UAEs will be reported to another entity

Describe:

